The electronic files generated through data collection will be identified by code numbers only and kept in password-protected devices/servers, separate from identifying information and available only to project staff. This helps to ensure that no identifying information will be disclosed in the unlikely

event that computerized data are stolen or otherwise seen by unauthorized persons.) All identifying electronic data will be destroyed immediately after data analysis is completed. Signed consent forms and session videos will be kept for 3 years after study completion. De-identified electronic data will be kept indefinitely. NCCB participants may ask at any time to have recordings of their meetings destroyed by calling/e-mailing one of the Principal Investigators at the numbers provided in the informed consent forms.

Our interviewers are trained to watch participants carefully and will stop questioning if an individual appears uneasy. At every interview, participants will be informed that they may ask the interviewer to stop if they are feeling uncomfortable. Referrals to counselors are available if participants wish and trained clinical counselors are available at NJCRI in the event that someone may need immediate assistance, whether it is during data collection or during the intervention sessions.

[name], [name], and project director will be available by phone at all times in case an emergency occurs. Any adverse event will be reported to the IRB and funding agency within 24 hours. Through our NCCB collaboration, we have excellent relationships with the community, including community members and agencies that we can mobilize in case the need arises (e.g., access to providers that provide detox and emergency services, free legal support clinics, community members who learned from participants about their engagement in the study may reach out to us for help in case they know one of our participants may be in trouble).

In addition to this extensive network, we will collect data during the baseline and follow-up assessments to monitor participant safety. For instance, we will conduct the MINI suicidality screen and if we find anyone at risk, we will have the appropriate group clinician reach out to the participant individually and make sure they are linked to the mental health services they need.

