 - a. Possible discomfort from answering personal questions. If the participants experience such discomfort at any time, they are free to inform the interviewer or facilitator, and are free to withdraw from the program. Interviewers will be trained to observe signs of discomfort and check with participants if they want to continue. Licensed facilitators and peer facilitators are trained to address discomfort during the sessions and participants are able to leave whenever they need.
 - b. Discomfort or risk of minor or major substance withdrawal symptoms. This will be carefully assessed at the Clinical Screen and throughout the intervention. Monthly assessments will test levels of AIDU and suicidality. Staff at Integrity House, Inc. and NJCRI, as well as group facilitators are highly trained to recognize and recommend courses of action for current or potential withdrawal symptoms, and will consult with project director at Integrity House, Inc. Integrity House, Inc. offers a variety of substance abuse treatment services and staff there are fully trained to recognize and address signs of withdrawal. [name] will be available to consult with project director and the group facilitators via phone and e-mail, and she will provide on-going, remote clinical supervision and monitoring of each case. In the event of acute withdrawal symptoms or high risk behaviors (i.e., suicidal or homicidal ideation, intent, or plan), the facilitator will refer the participant to the appropriate staff at NJCRI for admission to inpatient or ambulatory detoxification. [name] and the project director will review each intake for risk of withdrawal symptoms, level of care needs, and appropriate action plan. Members of the NCCB who are service providers will be available to provide consultation to any challenges that may arise with participants. Member service providers include social workers experienced in the field of substance abuse.

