 - c. Clinical emergencies will be handled by the NJCRI treatment team of experienced staff under supervision of project director and at NJCRI under the supervision of [name] and [name], who will be available by phone to all facilitators. Appropriate assessments will be conducted; treatment options will be recommended and followed through as necessary. NJCRI routinely provide services to individuals with substance use disorders and they are fully equipped to address any potential emergencies either themselves or via referrals. NJCRI, project director, and the NCCB have longstanding relationships with all substance abuse treatment facilities in Newark, NJ. NJCRI project director or on-call service providers will be available 24 hours a day to handle health-related emergencies. Any adverse event will be reported to the appropriate authorities within 48 hours and immediate action will be taken to minimize the likelihood of it occurring again.

d. Non-Response to Intervention. Close monitoring during the intervention allows us to determine if a participant develops increased risk or withdrawal symptoms or need of a higher level of care. At any time during the course of the intervention, any acute medical issues, non-response to treatment, or reported or observed withdrawal symptoms will result in the facilitator's consultation with project director and/or [name] regarding appropriate course of action using NJCRI guidelines.

e. Relapse and Referral for Further Treatment. As the participant nears the end of the intervention, our intervention will include relapse prevention, and what to do in the event of relapse. Each participant therefore will leave the intervention with a plan for handling relapse during the follow-up period and beyond. If further treatment is indicated, we will provide the participant with several outpatient referrals. After the intervention, should the participant request a referral for treatment, study personnel will refer the participant to NJCRI where staff can provide appropriate care or referrals.

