f. Deterioration. Clients who are deteriorating during treatment will be reviewed by project director and [name]. Clients may be withdrawn from the study and/or referred to a higher level of care if they meet specific indicators of deterioration that will be discussed during clinical supervision (e.g., become suicidal, regularly arrives high to participate in group discussions, consistently displays disruptive behavior during group).

g. Potential harm done by involvement in *Community Wise* groups. Typically intervention groups lead to a positive outcome. However, given the sensitive nature of the topics we discuss, the diversity of the groups, and the innovative nature of the intervention, harm as a result of participation in *Community Wise* is possible. The facilitators, project director, and [name] will closely monitor the course of the intervention through ongoing data collection, observations, and weekly supervision and staff meetings to monitor and address any issues that may arise.

h. All cases will be monitored closely on a weekly basis by the responsible members of the research team ([name], project director, [name], NCCB, research assistants) and the facilitators. All participants will be supervised by the facilitators, at least one other clinical expert (including [name]), and by research assistants through coding of video sessions, ongoing data analysis, and weekly clinical and staff meetings.

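### DSMP item 2b names detoxification admission as the destination for suicidal or homicidal crisis as well as for acute withdrawal; the sentence should be split

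*Combined protocol and SAP*

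**What the plan says.** All DSMP items below are in section 20C of the combined protocol and SAP.

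Item 2b is introduced as a risk of withdrawal symptoms, but it also takes in suicidality: "Monthly assessments will test levels of AIDU and suicidality". Its operative sentence begins "In the event of acute withdrawal symptoms or high risk behaviors (i.e., suicidal or homicidal ideation, intent, or plan" and concludes that "the facilitator will refer the participant to the appropriate staff at NJCRI for admission to inpatient or ambulatory detoxification". The sentence before it gives facilitators remote clinical supervision of each case by phone and e-mail. The sentence after it says that a supervisor and "the project director will review each intake for risk of withdrawal symptoms, level of care needs, and appropriate action plan".

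Item 2c deals with emergencies in general: "Clinical emergencies will be handled by the NJCRI treatment team of experienced staff". It continues: "Appropriate assessments will be conducted; treatment options will be recommended and followed through as necessary". It also provides on-call cover 24 hours a day. Item 2f deals with deterioration: "Clients may be withdrawn from the study and/or referred to a higher level of care if they meet specific indicators of deterioration". It gives suicidality as an example, among "indicators of deterioration that will be discussed during clinical supervision (e.g., become suicidal".

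Outside the DSMP:

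- Section 19D treats suicidal ideation with intent or plan, and homicidal ideas, as clinical emergencies to be triaged and assessed under NJCRI's guidelines. It sends the reader to the DSMP for how they are handled.
- Sections 7F and 23 have a clinician contact anyone found at risk on the MINI suicidality screen and link him to mental health services.
- The appended NJCRI crisis intervention policy covers suicidal or homicidal threats in the building.

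**The concern.** A suicidal or homicidal man who is not withdrawing has no need of detoxification. He needs a risk assessment and, as indicated, mental health care. The item 2b sentence names neither, and it gives detoxification admission as the purpose of referral for him too.

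This is a safety rule meant to be applied in the moment by a group facilitator. Section 20A says trained peers lead half of the conditions, so the person applying it may hold no clinical license. If the sentence were followed to the letter, the referral could reach NJCRI labeled as a detoxification case, and the crisis could be recognized later than it should be.

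**Working it through.** No arithmetic applies. The check is a reading of the sentence against the other places that deal with the same event.

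**1. What the sentence requires.** Two triggers are joined by an *or*: acute withdrawal symptoms, and high risk behaviors. The bracket defines the second as suicidality or homicidality and does not require withdrawal. One action and one purpose follow for both. Read literally, a suicidal man without withdrawal is referred for detoxification.

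**2. Whether the case can arise.** The clinician's eligibility question on the clinical screening form accepts a lifetime or past-year disorder with drug use in the last year, or weekly use. A man with no current use can therefore enroll. Suicidality is reassessed monthly, so the plan expects to find some. Section 9 excludes unstabilized severe psychiatric disorder, which makes the case rarer at entry but does not prevent later onset.

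**3. The routes side by side.**

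| Place | Event covered | Route | Relation to item 2b |
|---|---|---|---|
| DSMP 2b | Acute withdrawal; suicidality or homicidality | NJCRI staff, for detoxification | – |
| Section 19D | Suicidal ideation with intent or plan; homicidal ideas | Triage and needs assessment; DSMP cited for detail | Does not fit |
| DSMP 2c | Clinical emergencies (suicidality not named; the link is section 19D's use of the term) | Assessment, then treatment options, by NJCRI or by referral | Compatible: can follow the handover |
| DSMP 2f | Deterioration, including becoming suicidal | Review; possible study withdrawal or higher level of care | Compatible: permissive |
| Sections 7F and 23 | Risk found on the MINI suicidality screen | Clinician outreach; mental health services | Compatible: additional |
| NJCRI crisis policy | Suicidal or homicidal threat in the building | Response team | Compatible: can run alongside |

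Item 2d also watches for increased risk and for need of more care, but it names neither suicidality nor homicidality.

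**4. Whether detoxification is the destination anywhere else.** Sections 7F and 23 mention detox providers as a general community resource, and the services questionnaire lists detox as an answer option. Neither makes it the destination for suicidality or homicidality. Item 2b alone does that.

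**5. Why this sentence carries weight.** Section 19D defers to the DSMP for detail. Within the DSMP, item 2b is the only item that names homicidal ideation, and the only one that tells the facilitator what to do about suicidal ideation. Item 2c names neither, and item 2f describes review by supervisors. The most specific instruction is the one with the unsuitable destination.

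**The case against.** The strongest reply has four parts.

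- **Context.** The item is about withdrawal, so a detoxification purpose is natural there, and emergencies have their own item, 2c. This explains how the wording arose. It does not remove the second trigger, which the sentence adds expressly.
- **The facilitator's act hardly changes.** Under either wording he hands the man to NJCRI staff, who decide on care. This stands, and it weakens the argument from unlicensed peers. What remains wrong is the purpose attached to the handover.
- **Safeguards.** Item 2b provides remote supervision and intake review, item 2c provides 24-hour cover, section 18D provides weekly supervision, and sections 7F, 18G and 20A place counselors and licensed clinicians at the site. These stand and limit the practical risk. They are not a reason to keep an incorrect instruction.
- **Material not seen.** The NJCRI triage guidelines that section 19D relies on are not set out in the text available, and they may give the right steps. For that reason nothing is claimed about what NJCRI staff do once they receive the man.

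Three stronger readings are tempting, and the documents support none of them. A reader might infer that the plan has no mental health route for suicidal participants; sections 7F, 19D and 23, items 2c and 2f and the NJCRI policy show that it has. A reader might infer that item 2b contradicts all of those places; apart from the poor fit with section 19D, they are routes that can operate alongside it. A reader might take every man in a peer-led condition as the number affected; that count measures neither crises nor uses of this sentence.

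**Conclusion.** Wrong as written: minor, on patient safety. One sentence joins two triggers to one destination, and the destination is wrong for suicidal or homicidal crisis without withdrawal. It also does not fit the triage and needs assessment in section 19D. It is most likely a drafting error, since suitable routes stand elsewhere in the same plan.

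The conclusion rests on the plain wording of item 2b and on the text available. The documents give no rate of suicidal or homicidal ideation without withdrawal, so no number of men harmed or at risk is estimated. Sample size, power, error rates and analysis are unaffected.

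**What to change.** Split the item 2b sentence into two rules.

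1. **Acute withdrawal symptoms.** Keep the present rule: referral to the appropriate NJCRI staff for inpatient or ambulatory detoxification.
2. **Suicidal or homicidal ideation, intent or plan.** The facilitator hands the man over at once to NJCRI clinical staff for risk assessment under item 2c and the triage guidelines cited in section 19D. The NJCRI crisis response applies to a threat in the building. He is linked to mental health services, and item 2f review follows if he becomes suicidal during treatment. Detoxification is added only if acute withdrawal is also present.

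The cross-reference in section 19D can stay, because its term for these events already matches item 2c. The cost is the wording of one sentence in the DSMP. No new service is needed: the appended NJCRI material lists mental health and psychiatric services and a response team, item 2c provides the on-call cover, and the peer training in section 18D already includes safety protocols.

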Master or doctoral level social workers or psychologists will conduct the clinical screens to assess participant eligibility. All recruitment will take place at Integrity House. Staff will be supervised by our co-investigator project director and the PI [name].

Inclusion criteria for the factorial experiment participants in the study will include:

- Men age 18 or older
- Residence in Essex County, NJ
- Willingness to be voice recorded during group sessions
- Ability to speak English
- Having a substance use disorder measured by the Global Appraisal of Individual Needs-Substance Problem Scale (GAIN-SPS).
- Having been released from incarceration in the past 4 years. This is due to research that shows that people are more likely to be re-incarcerated within the first 4 years of release from incarceration.

Exclusion criteria for RCT participants will include:

- Severe psychiatric disorders in the prior 6 months not stabilized (schizophrenia, depression with psychotic features, bipolar disorder, any psychosis), as measured by the MINI International Neuropsychiatric Interview 6 psychosis and suicidality modules
- Gross cognitive impairment as measured by the Mini Mental State Exam.
- Sexual identification as female

Inclusion criteria for the focus group participants in the study will include:

- Being randomly selected from the study's intent to treat sample
- Being willing to be voice recorded
- Having attended at least one intervention session

Inclusion criteria for the NCCB members include:

- Men and women age 18 or older
- Knowledge about Essex County, NJ
- Ability to speak English
- Being invited to become a NCCB member after a majority favoring vote

We will use a screening script and a signed consent form to obtain permission to conduct the screening and use the data as part of the study, regardless of establishment of final eligibility.

Participants will be informed that the information will be confidential and they can choose to stop participating at any time and we will destroy their data upon receiving their request. Note that voice recordings of Community Wise are exceptions as this will include data from entire groups of participants. We will only destroy voice recordings if there is reason to believe the recording has content that can put participants in danger of being hurt or re-incarcerated.

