Capacity Building Projects consist of projects created by the groups to address a community problem. The capacity building projects are designed to create collaborative efforts to overcome and dismantle marginalizing processes by building positive social and organizational relationships and community capacity through the development and implementation of community projects aiming to address social determinants of health.

Facilitation by both licensed clinician and peer facilitator will provide an opportunity to test not only the efficacy of delivering the intervention through peers but will also determine the cost effectiveness of peer delivery vs. licensed facilitators.

Prior to the being consented into the study at baseline, participants will have the opportunity to attend an orientation session where we will explain the research design, the different conditions available, the randomization process, and the risks and benefits of participation in the study. We will emphasize the difference between the intervention and the research (mainly group sessions and data collection sessions). We hope that this make the participants better informed about the study and minimize contamination by explaining the importance to keep their activities in each group private. Data will be collected in six waves and will include a baseline and five monthly follow-up interviews. These interventions were developed and pilot tested by our team. We will also randomly select 24 groups to participate in focus groups and provide their feedback about their experience participating in the intervention. We will randomly select one group per intervention condition and only participants who attended at least one intervention session will be eligible to participate. We will keep track of other services that participants seek during follow-up assessments and we will control for the impact of these services statistically.

Below is a table displaying research activities. Note that for follow-up, depending on which condition someone is randomized into, they may complete between 1 to 5 follow-ups post intervention, receiving \$20 per follow-up plus \$2.50 for each intervention session they attend. This occurs because of the variance in the number in intervention sessions among the different conditions.:

Activity	Cost per participant	Time	Professional Assigned
Clinical screens	\$10	30 minutes	Licensed NCCB clinicians
Baselines	\$20	90 minutes	

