Follow-ups during intervention	\$20 + \$2.50 per intervention group attended in the past month for a maximum of \$30 per follow-up	90 minutes	NCCB, research assistants
Focus groups	\$20	90 minutes	
NCCB Meetings	\$50	120 minutes	Online survey
NCCB retreat	\$100	4 hours	Research assistants

[figure not shown]
Below is a table summarizing the participation of 592 men in the different experimental conditions. Note participants may stop participating at any time or skip any sessions without penalty:

Study condition with number of sessions and total cost estimate to deliver each condition					
Experimental Condition	Critical Dialogue (CD)	Quality of Life Wheel (QLW)	Capacity Building Project (CBP)	Facilitated By*	# 120 minute sessions
1: CD alone	Present	Absent	Absent	LF	9
2: CD alone	Present	Absent	Absent	PF	9
3: QLW alone	Absent	Present	Absent	LF	6
4: QLW alone	Absent	Present	Absent	PF	6
5: CBP alone	Absent	Absent	Present	LF	6
6: CBP alone	Absent	Absent	Present	PF	6
7: CD+QLW	Present	Present	Absent	LF	12
8: CD+QLW	Present	Present	Absent	PF	12
9: CD+CBP	Present	Absent	Present	LF	12
10: CD+CBP	Present	Absent	Present	PF	12
11: QLW+CBP	Absent	Present	Present	LF	9
12: QLW+CBP	Absent	Present	Present	PF	9
13: Full intervention	Present	Present	Present	LF	15
14: Full intervention	Present	Present	Present	PF	15
15: Core component	Absent	Absent	Absent	LF	0

*LF = Licensed facilitator; PF = Peer facilitator

Below is a table describing the research process:

Figure 4: Study's procedures

RA = randomization; C=Conditions; FU=monthly follow-ups; G= intervention groups

Measures:

Clinical Screen: Mini Mental State Exam, MINI International Neuropsychiatric Interview 6 psychoticism and suicidality modules, and the Global Appraisal of Individual Needs-Substance Problem Scale (GAIN-SPS).

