i. Any research staff member who learns of an adverse event is responsible for reporting the event to the Principal Investigators (PI), who are in turn responsible for discussing the event to make a joint decision about whether the event is serious or non-serious. Events will be categorized as adverse or serious adverse according to NIH guidelines: "Adverse events (AEs) are defined as any untoward medical occurrence that may present itself during treatment or administration of an intervention, and which may or may not have a causal relationship with the treatment. Serious adverse events (SAEs) are defined as any medical occurrence that results in death; is life-threatening; requires inpatient hospitalization or prolongation of existing hospitalization; creates persistent or significant disability/incapacity, or a congenital anomaly/birth defects." As such, adverse events (AEs) occurring during the course of the study will be collected, documented, and reported to the PIs or a designated co-investigator. The occurrence of AEs will be assessed during the intervention phase of the study at baseline and each group visit through clinical observation. Each week a study investigator will review the AE Forms from the previous week for events that were reported as new or continuing. The study investigators will follow all AEs to the point of a satisfactory resolution. A study participant may be withdrawn from the study if the responsible

investigator or group facilitators determine it is the best decision in order to protect the safety of a participant. All AEs will be assessed to determine if they meet criteria for an SAE. If an AE meets criteria for serious adverse event (SAE), as defined by the FDA, they will be systematically evaluated at each clinic visit and treated in a similar fashion as AEs with regards to monitoring and reporting.

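### Staff may withdraw a man from the study partly for the outcome behaviour, and no supplied text keeps his follow-ups or his place in the AIDU comparison

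*Combined protocol and SAP*

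**What the plan says.** Section 20C gives two routes by which staff can withdraw a participant.

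- **Item f (Deterioration):** "Clients may be withdrawn from the study and/or referred to a higher level of care if they meet specific indicators of deterioration". The project director and one other named person review such cases. The three examples are becoming suicidal, consistent disruption in group, and a man who "regularly arrives high to participate in group discussions".
- **Item i (adverse events):** withdrawal from the study is allowed if the responsible "investigator or group facilitators determine it is the best decision in order to protect the safety of a participant".

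Both items refer to the study, not only to the groups. Section 10 plans a baseline and five monthly follow-ups.

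The nearest related text is as follows.

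- Section 9 lists, as a focus-group criterion, "Being randomly selected from the study's intent to treat sample". The term is not defined and is not linked to the AIDU analysis.
- Section 9 also says of a man who chooses to stop that "we will destroy their data upon receiving their request".
- Section 10 says of the orientation session, "We will emphasize the difference between the intervention and the research", and says that "participants may stop participating at any time or skip any sessions without penalty".

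On custody, sections 18B and 18D each say that no research is done with a man while he is incarcerated. Section 18B also describes follow-up interviews inside a facility, done by the local PI or the project director. Sections 9 and 19D allow such research only after an IRB amendment, and 19D names board (NCCB) members and research assistants as the data collectors.

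**The concern.** Section 5 says that only components that significantly reduce AIDU will be kept. If men seen to be using heavily leave follow-up because of that use, and leave more often where there are more sessions at which to be seen, the men still measured in the session-rich conditions use less on average. A component that adds sessions could then look helpful with no true effect. Interviews not held cannot be recovered at analysis, so the rule has to be settled before such withdrawals occur.

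Facilitator type is also randomised, and item i gives facilitators a say in withdrawal. That is a reason to record who decided. It is not evidence that the two types differ.

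**Working it through.** **1. Does any supplied text settle the matter?**

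| Text | Covers | Covers staff withdrawal? |
|---|---|---|
| Section 9, intent-to-treat sample | Focus-group selection | No |
| Sections 9 and 10, stopping and data destruction | The man's own request | No |
| Section 10 and recruitment tips, research distinct from intervention | What participants are told | No |
| Tracking sheets, dropout column | Date and stage recorded | No rule on follow-up or analysis |
| Section 19D, re-incarceration | Consent to later follow-up | No, a different event |

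**2. Exposure to the trigger.** The plan itself notes differing session counts when explaining the number of follow-ups: "This occurs because of the variance in the number in intervention sessions among the different conditions". From the section 10 table: QLW 6, CBP 6, CD 9, QLW+CBP 9, CD+QLW 12, CD+CBP 12, full 15. Core is taken as 3 (section 10 text and the core handout; the table prints 0).

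- CD present: (9+12+12+15)/4 = 12. Absent: (3+6+6+9)/4 = 6.
- QLW present: (6+12+9+15)/4 = 10.5. Absent: (3+6+9+12)/4 = 7.5. CBP is the same.
- Licensed v peer: equal by design.

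**3. Illustration of size.** The documents give no withdrawal rates, so every input here except the session counts and 592 is assumed. There is no true effect; 30% of men use on 20 days a month and 70% on 5; a heavy user is removed with probability p at each session; removed men are left out of an unadjusted last-visit comparison.

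- Heavy users remaining after s sessions: k = (1−p)^s. Heavy share: h = 0.3k/(0.7+0.3k). Cell mean: 20h + 5(1−h).
- False effect = mean of the four cells without the component minus mean of the four with it.
- SD = 15·√(0.3×0.7) = 6.87. With 592/2 = 296 per level, SE = 6.87·√(2/296) = 0.565.
- False-positive rate = Φ(−1.96+d) + Φ(−1.96−d), where d = effect/SE.

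Worked case, p = 0.02: cell means at 3, 6, 9, 12 and 15 sessions are 9.311, 9.128, 8.949, 8.775 and 8.606.

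- CD absent: (9.311+9.128+9.128+8.949)/4 = 9.129.
- CD present: (8.949+8.775+8.775+8.606)/4 = 8.776.
- Difference: 0.353 days.

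| Setting | p = 1% | p = 2% |
|---|---|---|
| CD, full attendance (days a month) | 0.183 | 0.353 |
| in SE | 0.32 | 0.62 |
| false-positive rate | 6.2% | 9.6% |
| CD, 50% attendance (days a month) | 0.093 | 0.184 |
| false-positive rate | 5.3% | 6.2% |
| QLW or CBP, full attendance (days a month) | 0.091 | 0.176 |
| CD, average of five monthly contrasts | 0.121 | 0.233 |
| CD, each man with at least one follow-up kept at his own mean | 0.008 | 0.015 |
| Men removed, of 592 | 15 | 29 |

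The two rows that credit earlier interviews assume weekly sessions, follow-ups at weeks 4, 8, 12, 16 and 20, and that a man removed at session j misses follow-ups from week j on. The participant handouts give different counts (CD+QLW and CD+CBP 15; QLW and CBP 9). With those, CD is 0.182 and 0.347, so the choice hardly matters. At p = 0.25% the CD effect is 0.047 days.

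**The case against.** **The silence may come from the file.** The consent pages were removed, and section 20C item 1 says that the freedom to withdraw is written in the consent form. Investigator-initiated withdrawal could be covered there too. This stands as a limit on the claim, which covers only the supplied text.

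**The wording may be loose.** Item a of the same plan speaks of leaving the program; item f says may and and/or, and requires review. An intent-to-treat sample is named, so the team may already mean to keep these men. That is plausible, but staff following items f and i as written could stop the interviews, and a label used for focus groups does not restore them.

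**The size depends on an unfavourable analysis.** This stands. A reader might infer a large bias in the component effects. The documents do not support that: they give no withdrawal rates and no completers-only, last-visit analysis. Keeping earlier interviews removes almost all of the effect. AIDU is measured at baseline, and under the fixed-use model baseline adjustment would remove the bias entirely; with month-to-month variation it would do so only in part.

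**Facilitator comparison.** A reader might also infer that the licensed v peer contrast is biased. Session counts are equal, item i concerns safety rather than use, item f cases are reviewed above the facilitator, and section 18D puts both types under the same weekly supervision. Nothing supplied suggests different withdrawal rates, so reporting them is enough.

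**Custody is a separate matter.** Agreed. Some of those passages can be read as a default, an exception and a procedure, but the section 18B interview procedure mentions no amendment and the named data collectors differ. No bias is claimed.

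**Conclusion.** The gap is real: a rule that partly turns on the outcome behaviour can, read literally, end follow-up, and exposure to it differs by condition. The supplied text does not say that follow-ups continue or that the man stays in the AIDU comparison. It also does not say that he is excluded, so the point is that loss is permitted, not that it is planned.

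The size is unknown and probably small. At 1–2% removal of heavy users per session, the false CD effect is about 0.1–0.35 days a month at the last follow-up, the lower end being at half attendance, with a false-positive rate of about 5–10%. QLW and CBP effects are about half as large. These figures ignore clustering by group and ordinary dropout. The bias is negligible if withdrawals are rare or if each man's earlier interviews are kept. The change is worth making because it is cheap and lost interviews cannot be recovered.

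**What to change.** Leave the clinical withdrawal criteria and decisions in items f and i unchanged. Add a data rule to section 20C:

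- Withdrawal by staff ends the groups but not data collection.
- The man is offered his remaining monthly follow-ups unless he withdraws consent or the interviews themselves are judged a safety concern (section 20A notes that data-collection questions can disturb participants).
- Data already collected are kept unless he asks for their destruction, as section 9 allows.
- He is analysed as randomised.
- The reason and who decided are recorded, and withdrawals are reported by condition and by facilitator type.

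The cost is one IRB amendment, two recorded fields and one table, with some harder-to-reach follow-ups. If the consent form already covers this, the amendment need only bring the two texts into line.

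Separately, reconcile the custody passages in sections 9, 18B, 18D and 19D: whether and when a follow-up may be held in a facility, and who collects it.
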